## 4.0 Study Endpoints

Change in fMRI brain response.

## 5.0 Inclusion and Exclusion Criteria/ Study Population

### Inclusion Criteria

1. Age 18-65
2. English fluency
4. Meet criteria for cocaine use disorder (CUD), as determined by DSM-V criteria, using the Structured Clinical Interview for DSM-V.
5. Enrolled in an intensive outpatient treatment program (MUSC Center for Drug and Alcohol Programs Intensive Outpatient Program (CDAP-IOP), currently engaged in treatment for substance related problems, or interested in seeking treatment for substance related problems.
6. Able to read and understand questionnaires and informed consent
7. Lives within 50 miles of the study site.
8. Is not at elevated risk of seizure (i.e., does not have a history of seizures, is not currently prescribed medications known to lower seizure threshold)
9. Does not have metal objects in the head/neck.
10. Does not have a history of traumatic brain injury, including a head injury that resulted in hospitalization, loss of consciousness for more than 10 minutes, or having ever been informed that they have an epidural, subdural, or subarachnoid hemorrhage.
11. Does not have a history of claustrophobia leading to significant clinical anxiety symptoms.

### Exclusion Criteria

1. Past head injury or primary neurological disorder associated with MRI abnormalities, including dementia, MCI, brain tumors, epilepsy, Parkinson's disease, or demyelinating diseases
2. Any physical or intellectual disability affecting completion of assessments
3. Any contraindication to MRI
4. Current or past psychosis
5. ECT in last 6 months
6. Among females, pregnancy at screening will be exclusionary. Females of child bearing potential must agree to undergo a pregnancy test 72 hours prior to the fMRI scanning session and regularly before and during the medication trial. They must further agree to notify the study physician or PA if they become pregnant during the study.
7. Clinical Institute Withdrawal Assessment (CIWA-Ar) scale will be used to assess alcohol withdrawal. Individuals with CIWA > 8 will be excluded.

8. Individuals with unstable medical illness (e.g., hypertension, diabetes, myocardial infarction)
9. Has current suicidal ideation or homicidal ideation.
10. Has the need for maintenance or acute treatment with any psychoactive medication including anti-seizure medications and medications for ADHD
11. Suffers from chronic migraines
12. Any physical or intellectual disability affecting completion of assessments

We will not be enrolling vulnerable populations, specifically pregnant women, children, prisoners, or institutionalized individuals. We also will not enroll subjects incapable of providing their own consent. Should a potential subject present where there is a concern about their ability to understand study procedures and provide meaningful consent, their cognitive status and understanding of the study will be evaluated by [name] (Co-I). If there is any concern that the individual may be impaired, they will not be eligible for participation and not enrolled in the study. The rationale will be provided to the individual as well as his or her family members. Referrals for further evaluation, including urgent or emergent evaluation, will be made as needed and clinically warranted.

## **6.0 Number of Subjects**

Total enrollment number is 160. We plan to acquire full data sets from 144 individuals (24/group) to allow for a 10% rate of data loss due to motion artifacts in the MRI scanner. This will require 160 individuals to be invited to the consent/screening visit.

## **7.0 Setting**

All visits will take place on MUSC's campus at [name] at the Health Neuroscience Center and the Center for Biomedical Imaging.

## **8.0 Recruitment Methods**

Subjects for this study will be primarily recruited from the MUSC Center for Drug and Alcohol Intensive Outpatient Program (CDAP). Subjects interested in seeking treatment for substance related problems will also be recruited from advertisements consisting of flyers posted on the MUSC campus and the surrounding Charleston community, craigslist postings, posts on social media (i.e., Facebook, Instagram, and Twitter) and Trialfacts, as well as referrals for treatment to CDAP. Trialfacts will create compliant advertisements used in its recruitment strategy. Trialfacts creates a mobile and tablet friendly study web page, which is the central destination for all interested participants. Trialfacts promotes the study to its database of 60,000+ volunteers interested in participating in clinical trials. Trialfacts accesses highly targeted participant populations by searching online through social media, i.e. Facebook, Instagram, YouTube, Reddit, Quora, Craigslist, and Google searches. Trialfacts creates and manages an automated pre-screening questionnaire that participants complete to determine their eligibility. When a participant is deemed eligible based on their responses made in the pre-screening questionnaire, Trialfacts will notify the study staff immediately by sending an email with a password protected PDF attachment containing the participant's contact information. Once a participant passes the pre-screening, he/she will have the option of scheduling a time for a phone call with one of our research personnel. A separate email notification will then be sent when a participant books a time to receive a call from the study staff to schedule an in-person screening visit. All other information from potential participants' responses will be stored in a deidentified referral spreadsheet in a secure, encrypted Google Drive folder with restricted access to the study staff only. The first point of contact between the research team and potential participants will be at the first INTAKE visit day 1 (orientation) of the CDAP program or by telephone or email contact initiated by the subject. The research staff will talk to the individuals about the rationale for this research, explain the study, and encourage interested and comfortable individuals to sign up to participate. The exclusion criteria of this research study are designed to minimize risks to participants. Medical and psychiatric evaluations are extensive at the beginning of the trial, and these evaluations may be conducted at unscheduled times when clinically indicated for safety. Individuals who meet the eligibility criteria and sign up will be contacted for a screening visit (Study V1), which will be followed by an experimental visit 1 (Study V2) that will include a MRI. At experimental visit 2 (Study V3) individuals

will have an MRI before and after cTBS. Individuals will be followed up with by telephone 1 day, 1 week, 2 weeks and 3 weeks after their final visit (V3). An informed consent form which details the study requirements, risks, and benefits will be given to the potential research subject to read and sign.

## 9.0 Consent Process

We will obtain formal written consent from all new participants enrolled in this project. Following policies of the MUSC Institutional Review Board, written informed consent will be obtained and documented by the study's Research Coordinator before any study-related procedures are performed. Informed consent will be obtained in a private research office. A study coordinator will review study procedures and the consent form with each potential participant. Each individual may take as much time as they like to read the consent document and decide if they do or do not wish to participate. A decision not to participate will not affect their participation in other studies at MUSC, nor will it affect their access to health care at MUSC. [name] and research staff will review all screening material and determine study eligibility for each person.

## 10.0 Study Design / Methods

*Overview of study protocol.* The overarching goal of Project 4 within the COCA is to evaluate the efficacy of brain stimulation on addiction pathophysiology in corticostriatal circuitry, and to bidirectionally translate our findings with the preclinical COCA projects that are discovering molecular and physiological mechanisms of cue-induced drug seeking in animal models. Extending prior studies by our team and leveraging the intellectual resources of the COCA faculty, we will investigate the impact of active and sham cTBS on corticostriatal rsFC, drug cue reactivity and craving. This will be achieved through a double blind, active sham- and placebo-controlled study in cocaine users from the community or that have enrolled in an intensive outpatient treatment program (MUSC Center for Drug and Alcohol Programs Intensive Outpatient Program (CDAP-IOP)). Participants will be randomized to receive 3600 pulses of either active or sham cTBS alone without administration of any study medication. The study will require 3 visits while they are enrolled in the study. The cTBS sessions last 5 minutes and will occur immediately before their intensive outpatient visits. Clinical Assessments (see Assessments below) and neuroimaging data will be acquired at 2 timepoints: Baseline (V2) and immediately after cTBS (V3).

*Primary hypotheses:* Real mPFC cTBS will cause a larger decrease in cocaine cue-evoked functional connectivity than sham cTBS. The relationship between baseline rsFC and changes in rsFC will also be investigated as factors that mediate the effects of cTBS cocaine cue reactivity in the striatum and craving.

*Participants.* We plan to acquire full data sets from 144 individuals (24/group) to allow for a 10% rate of data loss due to motion artifacts in the MRI scanner. This will require 160 individuals to be invited the Consent/Screening Visit (V1)(see Targeted Enrollment Plan, Inclusion of Women & Minorities). This is based on a 66% eligibility rate from V1 (screening) to V2, followed by a 90% retention rate from V2 to V3. These enrollment and retention rates are based on prior studies by [name] in cocaine users which have used the MUSC Intensive Outpatient Program as a recruitment source (R01DA036617, R21DA041610). Treatment-seeking cocaine-dependent men and women, 18- 65 years old will be enrolled through the MUSC intensive outpatient substance abuse treatment program (see below) or their own initiated contact from study recruitment advertisements and randomized to receive either real or sham cTBS (stratified by gender). Randomization is appropriate for this sample [14] and therefore used to assign participants to experimental arms.

*MUSC Intensive Outpatient Treatment Program.* (More details of this program are found in Resources). Briefly, the program consists of 20 total treatment days (4 hours/day), spread across 4-5 weeks. Participants attend daily individual and group therapy sessions with staff certified in Cognitive Behavioral Therapy, contingency management, motivational interviewing and other established addiction treatment practices. Approximately 8-10 cocaine dependent individuals enroll in the Intensive Outpatient Program each month (60% male, 84% between the ages of 21-45, 10% of whom are court-ordered). The retention

rate for cocaine dependent individuals is 72% for the 4-week outpatient program, with 60% attending 1 month and 44% attending 2-month Accountability/Continuity visits. Participants will not be exclusively recruited from this treatment program – they will also be recruited from the community as we intend to enroll any adult that meets inclusion criteria.

Power analyses for study Aim 1—effects of cTBS on corticostriatal rsFC and cue-reactivity—were based on pilot data from a sham-controlled crossover study in which interleaved TMS/MRI was used to assess functional connectivity in cocaine users immediately before and after they received real or sham mPFC cTBS (see Significance). In these preliminary data in 12 cocaine users, real cTBS resulted in a larger effect on BOLD signal in the medial prefrontal cortex (eigenvalues real cTBS  $0.62 \pm 0.24$  vs. sham cTBS  $0.33 \pm 0.44$ ; Cohen's  $d=0.72$ ). Subjects will be assessed at 2 time points (m) with an anticipated interclass correlation coefficient (ICC) of 0.8 for the within subjects measures. The design effect accounts for multiple correlated observations within each subject, is estimated to be 1.8 (DE=  $[1+(2-1)0.8]$ );[15]. To allow for a 10% rate of data loss due to motion artifacts in the MRI scanner we have planned to enroll 160 individuals.

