## 1.0 Objectives / Specific Aims

A primary cause of relapse to cocaine use is the high motivation to seek drug produced by cocaine-associated cues. Cue-induced craving is associated with cue-induced elevated corticostriatal activity. Preclinical models demonstrate that decreasing activity in the medial prefrontal cortex (mPFC) and ventral striatum (i.e. nucleus accumbens core), henceforth the “corticostriatal circuit,” can block cue-induced cocaine seeking. As an extension of these preclinical data, the scientific premise of Project 4 is that targeted inhibition of the corticostriatal circuit will dampen cue-induced cocaine craving in individuals with cocaine use disorder.

The overarching goal of this project is to evaluate the efficacy of continuous theta burst stimulation (cTBS) as a tool to restore corticostriatal circuitry function and dampen cocaine cue reactivity among treatment-engaged individuals. cTBS is a non-invasive brain stimulation tool that induces long-term depression (LTD) of neural excitability in the area stimulated and in monosynaptic targets. Recent data from our group demonstrates that a single dose of cTBS to the mPFC selectively decreases activity in the ventral striatum and craving. The efficacy of cTBS as a tool to modulate the striatum depends upon connectivity between the frontal cortex and the striatum. Specifically, the experiments described in this proposal will determine if LTD-like cTBS delivered over mPFC decreases cocaine cue reactivity in individuals with cocaine use disorder. We will evaluate our novel intervention through a double blinded (ACTIVE cTBS vs. SHAM;) study in 160 cocaine dependent individuals. The chance of being randomly assigned to any given group within one of the two treatment arms is 1:1. All individuals will undergo a screening visit (Visit 1; V1), and a baseline fMRI visit (Visit 2; V2) that will assess rsFC and drug cue-reactivity. Following Visit 2, individuals will be randomly assigned to one of 2 to receive either: 1) Active cTBS alone, or 2) Sham cTBS alone. Both groups of participants will undergo a second fMRI visit (Visit 3; V3) that will assess resting-state and drug cue-reactivity: once at the beginning of the session and again immediately following Active cTBS or Sham cTBS. Research staff will follow-up with participants via phone to assess current drug use and craving at 1-day, 1-week, 2-week and 3-weeks post-V3.

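### At the plan's own rates, 160 people at the consent visit yield about 95 completers, not 144; define what 160 counts and remove the six-group figures

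*Combined protocol and SAP*

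**What the plan says.** Section 6.0 opens with "Total enrollment number is 160". It continues: "We plan to acquire full data sets from 144 individuals (24/group) to allow for a 10% rate of data loss due to motion artifacts". It then says: "This will require 160 individuals to be invited to the consent/screening visit". The Participants paragraph of section 10.0 repeats the 144, the 24 per group and the V1 count ("This will require 160 individuals to be invited the Consent/Screening Visit (V1"), and adds the basis: "This is based on a 66% eligibility rate from V1 (screening) to V2, followed by a 90% retention rate from V2 to V3".

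Other sections use the same numbers differently:

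- Section 1.0 describes a double-blind "study in 160 cocaine dependent individuals".
- The power paragraph of section 10.0 attributes the number to motion loss alone: "in the MRI scanner we have planned to enroll 160 individuals".
- The Visit 1 procedures in section 10.0 put consent before official enrolment.
- Section 13.0 gives the number enrolled as 144, not 160.

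On the design, section 1.0 says that after Visit 2 "individuals will be randomly assigned to one of 2 to receive either" active or sham cTBS, with 1:1 allocation. Section 12.0 nevertheless plans a preliminary intent-to-treat analysis of six groups, to supply effect sizes for a later trial.

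**The concern.** The 66% and 90% rates are given as the reason why 160 people at V1 are enough for 144 full data sets. Multiplied out, they do not produce 144. Section 6.0 uses 160 both for total enrolment and for attendance at the consent visit, which cannot both hold when a third of those screened are expected to be ineligible.

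The practical stake is when recruitment stops. Staff could stop at 160 consents or continue to about 243. Because randomisation follows V2, screen failures reduce the randomised sample directly. No single analysable number per arm can be read from the plan. The power paragraph gives no alpha, target power, required sample size or use of the 1.8 design effect, so a reader cannot judge whether the smaller number would be adequate.

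The leftover six-group figures add to this. The per-group number does not describe either arm, and the section 12.0 analysis refers to groups that the design does not contain.

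**Working it through.** **Inputs.** 160 at V1 and 144 full data sets (sections 6.0 and 10.0); 66% eligibility from V1 to V2 and 90% retention from V2 to V3 (section 10.0, Participants); 10% motion loss (sections 6.0 and 10.0); two arms at 1:1, randomised after V2 (section 1.0); d = 0.72 and design effect 1.8 (section 10.0, power paragraph).

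**Reproducing the plan's figure.** 160 × 0.90 = 144, or equally 144 / 0.90 = 160. This uses one 10% loss and no eligibility loss. With 90% retention, the implied eligibility rate is 144 / (160 × 0.90) = 1.00, against the stated 66%.

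**Applying the stated rates under each reading of 160**

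| Step | 160 consented at V1 | 160 enrolled at V2 |
|---|---|---|
| At V1 | 160 | 160 / 0.66 = 242.4, so 243 |
| At V2 | 160 × 0.66 = 105.6, about 106 (53 per arm) | 160 (80 per arm) |
| Completing V3 | 105.6 × 0.90 = 95.0 (about 48 per arm) | 160 × 0.90 = 144 (72 per arm) |
| If motion loss is separate | 95.04 × 0.90 = 85.5, about 86 (43 per arm) | 144 × 0.90 = 129.6, about 130 (65 per arm) |

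Like for like, the first column is 66% of the second (95/144; 86/130).

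**A third branch.** Suppose 144 is the number left after motion loss, and V2-to-V3 dropout is a second loss. Then 144 / 0.90 = 160 must complete V3, 160 / 0.90 = 177.8 (about 178) must reach V2, and 144 / (0.66 × 0.90 × 0.90) = 269.4, so 270, must attend V1. Here 160 is neither the V1 nor the V2 count.

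**Groups.** 6 × 24 = 144. With two arms, 24 per group is 48 people, and 144 people is 72 per arm.

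**Power, for context.** Two-sample t-test, d = 0.72, two-sided 5% (my assumption, since the plan states no alpha). The plan does not say how the 1.8 enters, so three uses are shown by effective number per arm.

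| Effective n per arm | 72 | 65 | 48 | 43 |
|---|---|---|---|---|
| n / 1.8 | 0.89 | 0.86 | 0.73 | 0.68 |
| n (no design effect) | 0.99 | 0.98 | 0.94 | 0.91 |
| 2n / 1.8 (two observations per subject) | 0.995 | 0.99 | 0.96 | 0.94 |

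The effect detectable with 80% power at 72, 48 and 43 per arm is 0.63, 0.78 and 0.83 with n / 1.8, or 0.47, 0.58 and 0.61 with no design effect.

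**The case against.** The strongest reply is that 160 means enrolled, and only the V1 label is misplaced. Sections 1.0 and 6.0 and the power paragraph all support this, consent comes before official enrolment, and 160 × 0.90 = 144 is then exact. This is a plausible account of what was intended, but it does not make the text consistent. Two sections put 160 at the consent visit, the screening number of about 243 is missing, section 13.0 enrols 144, and it stays unclear whether motion loss and dropout are one 10% or two.

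The power consequence is limited, and that stands. Power falls below 0.80 only when subjects are divided by 1.8. The pilot means and standard deviations as printed (0.62 ± 0.24 and 0.33 ± 0.44) give d = 0.29 / √((0.24² + 0.44²)/2) = 0.82 with the usual pooled SD. At that value the harshest use of the 1.8 still gives about 0.83 at 48 per arm and 0.79 at 43. The pilot was a crossover, so 0.72 may rest on a different standardisation; I used the plan's figure.

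The six-group analysis is labelled preliminary, and section 12.0 elsewhere compares real with sham, so the main comparison is unaffected. That limits the harm, but the planned analysis still cannot be run.

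Section 10.0 also points to a Targeted Enrollment Plan that is not in the text available to me. It may define 160, but it would not remove the conflict within the paragraph that cites it.

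**Conclusion.** The concern holds, and the sample-size statement must be corrected. With 160 at V1, the plan's rates give about 95 completers, 49 fewer than stated (34%), or about 86 usable if motion loss is separate. The figure of 144 needs 160 at V2 and about 243 at V1, which the plan does not say. The 24 per group and the six-group analysis contradict the two-arm design.

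The headcount result uses only the plan's own numbers. The power figures also assume a two-sided 5% test and take d = 0.72 as given; they show a problem under only one of three uses of the design effect. None of this forecasts accrual: the rates come from earlier studies that recruited through the outpatient program, and this trial also recruits from the community.

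**What to change.** Define 160 once, either as consented at V1 or as enrolled at V2. Say whether the 10% motion loss and the 10% loss between V2 and V3 are one loss or two, and carry all rates through a single funnel.

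- **Option A, 160 consented.** Restate about 106 at V2, about 95 completers and 86 to 95 analysable (43 to 48 per arm), with the effect detectable at that number. This needs no extra participants. The cost is a smaller stated sample and less precision.
- **Option B, 160 enrolled.** Correct the V1 wording in sections 6.0 and 10.0, state that about 243 will be screened, and give 144 completers (about 130 analysable if motion loss is separate). Compared with stopping at 160 consents, this means about 83 more screening visits (243 − 160), 54 more baseline MRI visits (160 − 106) and 49 more completed V3 sessions (144 − 95).

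If the sponsor means 144 to be what remains after two separate losses, neither option fits, and the V1 number is about 270, or 110 more than 160.

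Under any option, replace the 24 per group with a number per arm, and replace the six-group analysis in section 12.0 with one intent-to-treat real-minus-sham estimate and its confidence interval. State alpha, target power and how the 1.8 is applied. Then bring sections 1.0, 6.0, 10.0, 12.0 and 13.0 into agreement. The choice between options is the sponsor's.

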- Resting-State Functional Connectivity (24 min). The resting-state scan consists of four 6-minute runs. The first two runs will occur just prior to the cocaine cue reactivity task and the last two resting-state runs will occur immediately after the cocaine cue reactivity task. All participants will be asked to keep their eyes open and to not fall asleep. Participant's wakefulness during resting-state scans through the use of a) respiratory and heart rate signal and b) eye movement monitoring, in order to ensure participants are not sleeping. Data processing. Resting-state functional connectivity (rsFC) will be assessed using the in-house scripts with MATLAB and FSL. First, experimental design variables, pre-processed functional images filtered with a 0.01 to 0.08 Hz band-pass filter, and segmented images will be uploaded into the toolbox. 5-mm radius spheres will be created around a priori regions of interest (ROIs) (nucleus accumbens,

mPFC). Individuals' WM and CSF templates, heart-rate (HR), respiration rate and movement parameters will be included as covariates. rZ scores for each person will be generated and entered into statistical models.

- Functional MRI Cocaine Cue Reactivity Task (24 min). This task has been used in 4 original research publications by our group and reliably activates orbitofrontal and medial prefrontal regions [26-28]. They will receive two 12m runs of the task (randomized, counterbalanced order within groups). During both runs they will be instructed to 'allow' themselves to crave (passive limbic engagement). When the task begins participants are shown pseudorandomly interspersed blocks of images: 1) cocaine images (COC), 2) neutral images (NEU), and 3) pleasant images (PLE), all NEU and PLE images will be chromatically matched to the COC images. Stimuli are presented in six blocks across two runs, with each block lasting 3 min and 43 sec per image type (two blocks each of COC, NEU, PLE). Each block is followed by a 6-s washout period, allowing the hemodynamic response from the previous block to decline before the next is presented. Scanning parameters: Multislice gradient-echo echo planar imaging (TR=2000, TE=36 msec, field of view of 207 mm, voxel size 2.0 x 2.0 x 2.0 mm, 69 slices, 2 mm thickness, no skip).

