**Methods and analysis:** Using a standardized cocaine cue-reactivity paradigm we will quantify the percent BOLD signal change in the mPFC and the striatum (dorsal and ventral) as well as several other brain regions with known roles in salience (anterior insula & anterior cingulate), drug cue reactivity, and executive control. This will be achieved by extracting the average BOLD signal timecourse and the percent signal change during the cocaine cue versus neutral cue blocks from *a priori* anatomically defined regions of interest (ROIs), including the striatum (ventral striatum and dorsal striatum), insula, inferior frontal gyrus, and anterior cingulate cortex. Ventral striatal and dorsal striatal ROIs are derived from the FSL Oxford-GSK-Imanova striatal atlas, mapped via probabilistic diffusion tractography [34] in agreement with anatomical projection zones from the frontal cortex [35]. Percent signal change in these areas will be compared between groups receiving real versus sham cTBS (Aim 1). These data will be interpreted relative to changes in a positive (auditory cortex) and a negative (primary visual) control region. We will also perform a whole brain seed-based connectivity analysis with the area under the coil as our seed of interest.

**Alternative outcomes:** Known factors that contribute to variability in brain stimulation treatment response include gender and age (Ziemann & Sieber 2010). Variance in these factors may preclude the detection of a true positive. Consequently, these factors will be included as covariates in the analyses. The scalp-cortex distance will be calculated using Standardized automatic segmentation software developed by our laboratory (BrainRuler 1.0, MATLAB Central repository open source) [36]. From an exploratory hypothesis-generating perspective, for Aims 1 & 2 we will also perform whole brain psychophysiological interaction analyses to evaluate if there are other neural areas that are modulated by TBS that we would have missed in our primary ROI-based strategy.

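### Programme patients and people outside the programme are pooled, but treatment setting is neither a stratification factor nor a covariate (minor; mainly affects craving and follow-up drug use)

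*Combined protocol and SAP*

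**What the plan says.** **Who is pooled.** Inclusion criterion 5 (Section 5.0) admits programme enrollees and also people "currently engaged in treatment for substance related problems, or interested in seeking treatment for substance related problems". Section 10.0 says of the programme's patients and others that "they will also be recruited from the community as we intend to enroll any adult that meets inclusion criteria". Section 8.0 describes recruitment as mainly from the programme. Section 15.0, under protection against risks, describes it as from the general community through advertising. No share is given for either stream.

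**How the streams differ.** Section 10.0 states that "the program consists of 20 total treatment days (4 hours/day), spread across 4-5 weeks", with daily individual and group therapy. The plan gives no treatment content for anyone outside the programme.

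**Randomisation.** Section 10.0: participants are "randomized to receive either real or sham cTBS (stratified by gender". No other stratum is named.

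**Covariates.** Section 12.0, under alternative outcomes: "Known factors that contribute to variability in brain stimulation treatment response include gender and age", and "Consequently, these factors will be included as covariates in the analyses". Two other items might be taken for adjustment. In the resting-state processing (Section 10.0), "WM and CSF templates, heart-rate (HR), respiration rate and movement parameters will be included as covariates", but these clean the imaging signal and carry no information on setting. Section 12.0 also says that "The scalp-cortex distance will be calculated using Standardized automatic segmentation software developed by our laboratory", without saying that it enters a model. The baseline clinical measures taken at Visit 1 are reserved for post-hoc use.

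**The concern.** Someone in a 4-hour-a-day programme and someone only interested in treatment may differ in recent use, craving and later drug use whatever stimulation they receive. Criterion 5 has to be checked at screening, and Section 1.0 places randomisation after Visit 2, so setting can be known for everyone before allocation. Section 12.0 justifies gender and age on the ground that variance from known factors can hide a true effect. The same argument applies to setting, which is left out.

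Two things are at stake. If setting predicts an outcome, leaving it out of the model keeps that variance in the error term. If the arms happen to differ in programme share, the plan has no pre-specified way to allow for it, and adding setting after an imbalance has been seen would be a data-driven choice. Both matter most for craving and for drug use reported by telephone from 1 day to 3 weeks after Visit 3.

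The session context is also unclear. The overview in Section 10.0 places cTBS immediately before the intensive outpatient visit, and the Visit 3 procedures place it before group therapy. Participants outside a programme would have no such visit.

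**Working it through.** The plan gives no figure for the effect of setting or for the mix, so everything below is illustration under stated assumptions.

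**Numbers per arm**
- Section 6.0 plans 144 complete data sets: 144 / (1 - 0.10) = 160, which reproduces the plan's enrolment. With two arms, 144 / 2 = 72 per arm.
- The eligibility and retention rates in Section 10.0 give 160 x 0.66 x 0.90 = 95 completers, or about 47 per arm. Which figure is right is a separate matter, so both are carried.

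**Assumptions**
- Programme share p: 0.5 as the base case, 0.8 as a variant because Section 8.0 says recruitment is mainly from the programme.
- Setting difference δ on an outcome: 0.5 or 0.8 within-setting SD.

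**Chance imbalance** (normal approximation, setting ignored in the randomisation)
- SE of the difference in programme share = sqrt(2p(1-p)/n).

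| p | n per arm | SE | 95% range | P(gap > 10 points) |
|---|---|---|---|---|
| 0.5 | 72 | 0.083 | ±16 points | 23% |
| 0.5 | 47 | 0.103 | ±20 points | 33% |
| 0.8 | 72 | 0.067 | ±13 points | 13% |
| 0.8 | 47 | 0.082 | ±16 points | 23% |

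An exact hypergeometric calculation at p = 0.5 gives 24% at 72 per arm and 31% with 95 completers for a gap of at least 10 points.

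**What a gap does to an estimate**
- Shift = gap x δ. A gap of 15 points or more arises in about 7% of randomisations at 72 per arm. A 15-point gap moves the estimate by 0.15 x 0.5 = 0.075 SD or 0.15 x 0.8 = 0.12 SD.

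**Variance removed by adjustment**
- Share = p(1-p)δ² / (1 + p(1-p)δ²).
- p = 0.5, δ = 0.5: 0.0625 / 1.0625 = 6%.
- p = 0.5, δ = 0.8: 0.16 / 1.16 = 14%.
- p = 0.8, δ = 0.8: 0.1024 / 1.1024 = 9%.

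**Power** (two-sided 0.05 assumed, 72 independent participants per arm, p = 0.5)
- Power = Φ(d·sqrt(n/2)/s - 1.96), with s = sqrt(1 + 0.25δ²) unadjusted and s = 1 adjusted.
- At the pilot d = 0.72: 98% (δ = 0.8) or 99% (δ = 0.5) unadjusted, 99% adjusted.
- At d = 0.47, the effect detectable with about 80% power: 74% (δ = 0.8) or 78% (δ = 0.5) unadjusted, about 80% adjusted.

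**The case against.** The strongest reply is that the endpoint in Section 4.0 is change in fMRI response, measured before and after one 5-minute session at a single visit. A stable difference between settings largely cancels in within-person change. The behavioural assessments paragraph in Section 10.0 says that one session is not expected to move craving, mood or use, and that brain measures are primary for that reason. No confirmatory test is planned for the follow-up data. This stands, and it is why the point is minor.

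A second reply is that the size depends on assumptions. A 50:50 mix fits poorly with recruitment mainly from the programme, and at 80:20 both the imbalance and the variance gain shrink. At the pilot effect with 72 per arm, adjustment hardly changes power. This also stands.

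A third is that time-line follow-back, urine screen and craving inventory at Visit 1 already capture recent use and craving. This stands only in part, because they are reserved for post-hoc analyses.

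A reader might also infer three stronger things that the documents do not support:
- That a chance imbalance could pass for a cTBS effect as a form of bias. Under 1:1 randomisation it is already covered by the type I error rate.
- That setting is the largest difference between participants. The plan ranks no differences.
- That programme therapy spans the scans and the whole 3-week follow-up. The visit intervals are not fully given, and programme retention is stated as 72%.

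**Conclusion.** The omission is real. Setting can be known before allocation, and the plan's own reason for using covariates applies to it. It does not bias the comparison of real with sham cTBS, and the gain for the primary within-session fMRI change is probably small.

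The benefit lies in craving and follow-up drug use: about 6-14% of outcome variance for setting differences of 0.5-0.8 SD at a 50:50 mix, and about 9% for 0.8 SD at 80:20. It also protects against gaps in programme share that exceed 10 points in roughly a quarter to a third of randomisations at 50:50. Setting differences, mix and, for power, effect size are assumptions, because the documents give neither the shares nor the influence of setting. The severity is minor: a nearly free improvement, not a defect in the primary analysis.

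**What to change.** - Record treatment setting at V2 as two levels: in the intensive outpatient programme, or not.
- Pre-specify it, before unblinding, as a covariate beside gender and age in the craving, follow-up use, cue BOLD and rsFC models.
- Tabulate arm by setting.
- For participants not yet randomised, setting may be added as a second two-level stratification factor. For those already randomised, the covariate is enough. A three-level factor crossed with gender would make six strata, which is not needed.
- Reconcile the statements in Section 10.0 that place cTBS before the outpatient or group therapy visit with the enrolment of people who have no such visit.

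The cost is one degree of freedom per model and, if setting is also stratified, four strata instead of two. The information should already be available from checking criterion 5, and the sample size does not change.
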